10. MEASUREMENT OF EFFECT

In this study, the study drug 5-ALA is not expected to have any direct effect on tumor cells. Future studies may be designed to investigate the potential of 5-ALA and its photosensitizing metabolite PpIX in a study of photodynamic therapy, but in this study no attempt will be made to photo-activate the tumor cells.

The study will look at the specificity and sensitivity of 5-ALA/PpIX for malignant glioma cells.

10.1 Definitions

Response and progression will be primarily evaluated in this study using MRI volumetric techniques which measure the volume of residual enhancing tumor.

10.1.1 Extent of Resection

Volumetric MRI techniques measure difference in the areas of bright MRI signal when a post-operative T1 non-enhanced image is compared to a post-operative T1 gadolinium enhanced image. These differences may be measured by postprocessing digital subtraction techniques (dsMRI – see section 2.4) or by outlining areas of new bright signal as judged by the neuroradiologist. Extent of resection is divided into three categories which are defined as follows:

- Gross-total tumor resection (GTR) of tumor is defined as no measureable residual contrast enhancement in the immediate post-operative MRI.

- Near-total resection (NTR) is defined as measureable post-operative residual contrast enhancement greater than or equal to the volume of one MRI voxel (0.175 cm³) and less than or equal to 2.5 cm³.
- Incomplete resection (IR) is defined as measureable post-operative residual contrast enhancement greater than 2.5 cm³.
- 10.2 Guidelines for Evaluation of Measurable Disease

All neuroradiological measurements should be taken and recorded in metric notation using standardized volumetric techniques. These techniques have been discussed previously.^{7,11,12}

- 10.3 Confirmatory Measurement/Duration of Response
 - 10.3.1 Confirmation N/A
 - 10.3.2 Duration of Overall Response N/A
 - 10.3.3 Duration of Stable Disease N/A

11. REGULATORY AND REPORTING REQUIREMENTS

Adverse event (AE) reporting for this study is via the FDA safety information and adverse event reporting system, Medwatch, FDA form 3500A. The descriptions and grading scales found in the revised NCI Common Toxicity Criteria (CTC) version 3.0 will be utilized for adverse event reporting and are available in the Clinical Research Department and available on line at http://ctep.cancer.gov/reporting/ctc.html. Expected adverse events specific for 5-ALA are found below (Section 11.1.2).

- 11.1 Expedited Adverse Event Reporting (AE; formerly known as Adverse Drug Reaction)
 - 11.1.1 Expedited Reporting Guidelines Phase 1 studies with investigational agents (Including hospitalization defined in bullet 1 below)
 - For Hospitalization only Any medical event equivalent to CTC grade 3, 4, or 5 which precipitated hospitalization (or prolongation of existing hospitalization) must be reported regardless of designation as expected or unexpected and attribution.
 - The FDA safety information and adverse event reporting system, Medwatch,
 FDA form 3500A will be used for reporting within 24 hours.
- 11.1.2 Agent-Specific Expected Adverse Events List

The list below guides the investigator in determining which AEs require expedited reporting. Those AEs that do not require expedited reporting are reported in routine study data submissions.

- Skin reaction Grades 1 and 2.
- AST/ALT elevation Grades 1, 2, or 3.
- Nausea Grades 1 and 2.
- 11.1.3 Other Expected Adverse Events

For this protocol, the following more serious expected adverse events are risks associated with surgical removal of a malignant brain tumor and do not require expedited reporting:

- Adverse reaction to anesthesia Both local and general anesthesia involve risk. There is a possibility of complication or injury from all forms of anesthesia and sedation.
- Balance problems Difficulty with balance or vertigo may occur as a result of the tumor itself or from the surgery to correct it. Nausea and vomiting may also occur after surgery.
- Bleeding It is possible, though unusual, to experience an episode of bleeding, which may be extensive during or after surgery. Bleeding may

- require additional treatment or transfusion. Certain medications, such as antiinflammatory drugs, may increase the risk of bleeding.
- Blood clot development Blood clots may occur with any type of surgery. Blood clots at the site of the surgery can block blood flow and cause complications, including pain, swelling, inflammation and tissue damage (stroke).
- Brain injury There is a risk that the procedure will cause injury of the surrounding brain. The symptoms that result from the injury depend on the location of the tumor.
- Cardiac complications There is a chance that having the procedure could cause an irregular heartbeat or a heart attack.
- Functional loss It is possible to experience problems such as difficulty opening the mouth or chewing after surgery. Also, speech, language and memory difficulties may occur after surgery.
- Hydrocephalus It is-possible that the normal flow of spinal fluid around the brain may be altered. Additional treatment, including surgery, may be necessary to correct this.
- Infection Infection may occur not only at the incision site, but also within the bone flap. Infection-related risks also include the development of meningitis (an infection which causes inflammation of the membranes covering the brain and spinal cord) or a brain abscess (localized collection of pus).
- Loss of nerve function Some loss of function may occur in the facial nerves as a result of the procedure.
- Paralysis it is possible that some paralysis or numbness may occur as a result of the surgery.
- Post-operative neurologic decline There is a small risk that neurologic function will decline following surgery and may produce such symptoms as personality changes or loss of cognitive function. These problems are sometimes caused by post-operative hemorrhage (bleeding into or on the surface of the brain) or cerebral edema (accumulation of fluid that results in swelling and pressure on the brain).
- Post-operative pain It is possible, though unlikely, that pain or other symptoms will increase following the procedure. A headache may linger anywhere from one week to one month following craniotomy and occasionally for a longer period of time.
- Recurrence There is a chance that the tumor may return to the same site. However, the risk of recurrence depends on the type of tumor and how much of it can be removed in the initial operation.
- Respiratory difficulties Breathing difficulties, which are usually temporary or post-operative pneumonia may occur as a result of surgery. Pulmonary embolus could occur from blood clotting in the veins.
- Seizure activity Abnormal electrical activity in the brain, which can trigger seizures, may develop in response to the tumor itself or its removal.
- Visual disturbances There may be some changes in visual function caused by the surgery or by the tumor itself.

26

UNEXPECTED EVENT		EXPECTED EVENT		
GRADES 2 – 3 Attribution of Possible,	GRADES 4 and 5 Regardless of Attribution	GRADES 1 - 3	GRADES 4 and 5 Regardless of Attribution	
Probable or Definite	Regulates of Attribution		regulates of Attribution	
Grade 2 - Expedited report within 10 working days.	Report by phone to IDB within 24 hrs. Expedited report to follow within 5 calendar days.	Adverse Event Expedited Reporting NOT required.	Report by phone to IDB within 24 hrs. Expedited report to follow within 5	
Grade 3 - Report by phone to IDB within 24 hrs.	This includes all deaths within		calendar days.	
Expedited report to follow within 10 working days.	30 days of the last dose of treatment with an		This includes all deaths within 30 days of the last dose of treatment with an	
(Grade 1 – Adverse Event Expedited Reporting NOT	investigational agent regardless of attribution.		investigational agent regardless of attribution.	
required.)	Any late death attributed to the agent (possible, probable, or definite) should be reported within 5 calendar days.		Any late death attributed to the agent (possible, probable, or definite) should be reported within 5 calendar days.	

- 11.1.4 Forms None additional
- 11.1.5 Secondary AML/MDS N/A
- 11.2 Data Reporting In addition to adverse event reporting, all reports will be provided to the FDA as required by the Code of Federal Regulations.
- 11.3 CTEP Multicenter Guidelines N/A
- 11.4 Cooperative Research and Development Agreement (CRADA)/Clinical Trials Agreement (CTA) N/A The agent, aminolevulinic acid (5-ALA), used in this protocol is provided by Collaborator, DUSA Pharmaceuticals New York, Inc., Valhalla, NY 10595.
 - 11.4.1 Aminolevulinic acid (5-ALA) may not be used for any purpose outside the scope of this protocol, nor can aminolevulinic acid (5-ALA) be transferred or licensed to any party not participating in the clinical study. Collaborator data for aminolevulinic acid (5-ALA) are confidential and proprietary to Collaborator and shall be maintained as such by the investigators.
 - 11.4.2 Any data provided to Collaborator(s) for Phase 3 studies must be in accordance with the guidelines and policies of the responsible Data Monitoring Committee (DMC), if there is a DMC for this clinical trial.
- 11.5 Data Safety Monitoring Plan

A minimum of 3 to a maximum of *18 subjects will be enrolled in this study. Oral 5-ALA will be administered 2-3 hours prior to surgery in cohorts of three at five escalating doses (10, 20, 30, 40, or 50 mg/kg). (*Due to four patients receiving 40mg/kg rather than three, 19 total patients will be studied in phase 1. Protocol deviation approved by IRB on 17 Oct 2013.)

Study investigators and study personnel will carefully screen each patient for side effects and adverse events. Expected adverse events specific for 5-ALA are described in the Protocol (Section 11.1.2) and other expected adverse events are

27

listed in Section 11.1.3. Subjects will be assessed for any unexpected serious adverse events such as significant changes in vital signs, nausea, vomiting, rashes, skin eruptions, and any long term changes in liver function. Unauthorized disclosure of protected health information is also a risk of this study.

It is the responsibility of the Principal Investigator (PI), [name] to oversee the safety of this Phase I study. However, since [name] holds the IND for the investigational drug, an independent data safety monitoring committee (DSMC) has been assigned to this study. The DSMC will consist of [name] (hematology/oncology physician), [name] (oncology research study specialist), and [name] (neuropsychologist).

The DSMC will meet after each cohort (every third subject) has received the study drug to assess safety data including side effects and fluorescence ratings. The DSMC will discuss each adverse event and determine causality in consultation with the Principal Investigator. In addition, the DSMC will review study progress (including data quality and timeliness, recruitment, accrual and retention); study procedures (including subject privacy and data confidentiality protection); outcomes of adverse events and any new literature to assess change to the risk/benefit ratio and to determine if modifications need to be made or the study terminated. If any serious adverse events or unanticipated problems are identified and determined to be associated with the study protocol, the study will be stopped and immediately reported to SCRIHS and the FDA. The DSMC has the authority to stop the study and take whatever steps are necessary to protect the safety and well-being of research subjects until the IRB can evaluate the DSMC's report.

Study personnel will be expected to immediately alert the DSMC to any unanticipated problems or serious adverse events. Unanticipated problems and adverse events will also be reported to SCRIHS in accordance with institutional policy (http://www.siumed.edu/adrfa/SCRIHS/AdverseEvent.pdf) and to the FDA as required. Reports generated by the DSMC will be provided to SCRIHS at the time of continuing review.

To ensure the integrity of the data collected from study participants several procedures will be implemented. All study personnel involved in data collection will be thoroughly trained in the assessment methods thus ensuring consistent applications of procedures and measurement consistency across study subjects. All data will be automatically saved to a computer hard drive and stored on a secure server (i.e., password protected) which is backed up daily. All informed consent documents will be kept at the study site in a separate locked file cabinet with restricted access. Issues related to data integrity will be discussed as a recurring agenda item in the bimonthly study team meetings.

The study coordinator is responsible for data security. Data management activities include: using double data entry and monitoring outliers. Data security measures include keeping hard copies of data double-locked at all times with access limited to investigators and approved study personnel using password protection and a secure server.

Reporting Adverse Events

We will follow 1996 and 2000 International Conferences on Harmonization, Sections E2 and E6 Good Clinical Practice and FDA regulations. An adverse event (AE) is

28

defined as any untoward medical occurrence that does not necessarily have a causal relationship with this treatment. A Serious Adverse Event (SAE) is defined as any untoward medical occurrence that results in death, is life-threatening, requires hospitalization or prolongation of hospitalization, results in persistent or significant disability/incapacity, or is a congenital anomaly or birth defect.

We will use the descriptions and grading scales found in the revised NCI Common Terminology Criteria for Adverse Events (CTCAE) Version 3.0 for AE reporting. All participating sites will have access to the CTCAE guide and it can be downloaded at http://ctep.cancer.gov

Expectedness - Adverse Events can be 'Unexpected' or 'Expected' for expedited reporting purposes only.

Attribution of the Adverse Event

1	Definite	AE is clearly related to the study treatment
2	Probable	AE is likely related to the study treatment
3	Possible	AE may be related to the study treatment
4	Unlikely	AE is doubtfully related to the study treatment
5	Unrelated	AE is clearly not related to the study treatment

Expedited Adverse Event Reporting – Phase 1 studies with investigational agents (Including hospitalization below):

- For Hospitalization only Any medical event equivalent to CTC grade 3, 4, or 5 which precipitated hospitalization (or prolongation of existing hospitalization) must be reported regardless of designation as expected or unexpected and attribution.
- The FDA safety information and adverse event reporting system, Medwatch, FDA form 3500A will be used for reporting within 24 hours.

Expedited Reporting Guidelines

 Medwatch Reporting Requirements for Adverse Events that Occur within 30 Days of the Last Dose of the Investigational Agent on Phase 1 Trials.

Phase 1 Trials						
	Grade 1	Grade 2	Grade 2	Grade 3	Grade 3	Grades 4 & 5 ²
	Unexpected and Expected	Unex- pected	Expected	Unexpected with without Hospitali- Hospitali- zation zation	Expected with without Hospitali- zation zation	Unexpected and Expected
Unrelated Unlikely	Not Required	Not Required	Not Required	10 Not Calendar Required	10 Not Calendar Required	24-Hour; 5 Calendar Days
Possible Probable Definite	Not Required	10 Calendar Days	Not Required	24-Hour; 24-Hour; 5 Calendar 5 Calendar Days Days	10 Not Calendar Required	24-Hour; 5 Calendar Days

Adverse events with attribution of possible, probable, or definite that occur greater than 30 days after the last dose of treatment with an agent under a CTEP IND require reporting as follows:

AdEERS 24-hour notification followed by complete report within 5 calendar days for:

- Grade 3 unexpected events with hospitalization or prolongation of hospitalization
- · Grade 4 unexpected events
- Grade 5 expected events and unexpected events

IRB NUMBER: 12-135

Although an AdEERS 24-hour notification is not required for death clearly related to progressive disease, a full report

Note: All deaths on study require both routine and expedited reporting regardless of causality. Attribution to treatment or other cause must be provided.

Expedited Adverse Event Reporting Timelines (Definitions)

- 24 hours; 5 calendar days The investigator must initially report the AE via Medwatch within 24 hours of learning of the event followed by a complete Medwatch report within 5 calendar days of the initial 24-hour report.
- 10 calendar days A complete Medwatch report on the AE must be submitted within 10 calendar days of the investigator learning of the event.
- Any medical event equivalent to CTCAE grade 3, 4, or 5 that precipitates
 hospitalization (or prolongation of existing hospitalization) must be reported
 regardless of attribution and designation as expected or unexpected with the
 exception of any events identified as protocol-specific expedited adverse event
 reporting exclusions.

Routine Adverse Event Reporting

All Adverse Events must be reported in routine study data submissions. AEs reported through Medwatch must also be reported in routine study data submissions.

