4.2 Definition of Dose-Limiting Toxicity

Dose-Limiting Toxicity (DLT) is determined by Adverse Events which are defined and graded following the CTEP, NCI Guidelines: Adverse Event Reporting Requirements of January 1, 2005

(http://ctep.cancer.gov/protocolDevelopment/electronic_applications/docs/newadverse_2 006.pdf) and the CTC/CTCAE Criteria. Expected Adverse Events (AE) have not been identified for 5-ALA by the NCI Comprehensive Adverse Event and Potential Risk list (CAEPR) but are identified in section 11.1.2 and 11.1.3 of this protocol. Those AEs which are determined to be Grade 2 or higher and directly attributed to 5-ALA or its metabolites will be considered to be dose-limiting for the purposes of determining dose escalation. At present, CTEP does not have a CAEPR or ASAEL for this agent (see Appendix D).

Since this study involves the one-time dose of the study drug, further dose modifications associated with the above adverse events will not be required.

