6.2 Adverse Event Characteristics

CTCAE term (AE description) and Grade

The descriptions and grading scales found in the revised NCI Common Terminology Criteria for Adverse Events (CTCAE) version 3.0 will be utilized for AE reporting. All appropriate treatment areas will have access to a copy of the CTCAE version 3.0. A copy of the CTCAE version 3.0 can be downloaded from the CTEP web site (http://ctep.cancer.gov).

Expectedness - AEs can be 'Unexpected' or 'Expected' for expedited reporting purposes only. 'Expected' AEs are listed in sections 11.1.2 and 11.1.3 of this protocol.

Attribution of the AE

Definite – The AE is clearly related to the study treatment.

Probable – The AE is likely related to the study treatment.

Possible – The AE may be related to the study treatment.

Unlikely – The AE is doubtfully related to the study treatment.

Unrelated – The AE is clearly NOT related to the study treatment.

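### Section 11.1.3 exempts surgical event types from expedited reporting with no attribution limit, so a listed Grade 2 or non-hospitalized Grade 3 event attributed to 5-ALA needs no expedited report, and the rules for hospitalized Grade 3 events conflict

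*Combined protocol and SAP*

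**What the plan says.** Section 6.2 says that Expected "AEs are listed in sections 11.1.2 and 11.1.3 of this protocol". The two lists differ in kind. Section 11.1.2 lists three drug effects, each with grade limits: skin reaction (Grades 1 and 2), AST/ALT elevation (Grades 1 to 3) and nausea (Grades 1 and 2). Section 11.1.3 lists events because surgery can cause them, and says that "the following more serious expected adverse events are risks associated with surgical removal of a malignant brain tumor and do not require expedited reporting". Its bullets include "Cardiac complications There is a chance that having the procedure could cause an irregular heartbeat or a heart attack", a bullet on neurologic decline ("There is a small risk that neurologic function will decline following surgery") and one on respiratory difficulties ("Breathing difficulties, which are usually temporary or post-operative pneumonia may occur as a result of surgery").

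In the table that follows 11.1.3, the entry for expected events of Grades 1 to 3 is "Adverse Event Expedited Reporting NOT required", with no condition on attribution. The table in 6.3.2, repeated in 11.5, separates expected from unexpected even in its row for Possible, Probable and Definite relation.

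Section 4.2 provides that events "Grade 2 or higher and directly attributed to 5-ALA or its metabolites will be considered to be dose-limiting". It makes no exception for event types in 11.1.3.

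**The concern.** Whether an event is expected for the drug and whether it can also follow a craniotomy are different questions. The protocol merges them. An arrhythmia, seizure or neurologic decline that the investigator attributes to 5-ALA is not among the drug effects in 11.1.2. It is nevertheless handled as expected, because surgery can cause the same kind of event.

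Establishing a safe dose is a primary objective (1.1.1). A DLT of a kind not listed for the drug is the sort of event for which the protocol otherwise sets short deadlines. Here it can be reported on the routine schedule.

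**Working it through.** No sample size, power or error rate bears on this point. The check is a count and a trace through the reporting rules.

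**Scope of the list.** The bullets in 11.1.3 are: anesthesia reaction, balance problems, bleeding (3); blood clot, brain injury, cardiac complications, functional loss, hydrocephalus, infection, loss of nerve function, paralysis, neurologic decline, pain, recurrence, respiratory difficulties (12); seizure, visual disturbances (2). The total is 3 + 12 + 2 = 17.

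**Trace of a related event.** Take an event rated Possible, Probable or Definite. Compare its handling if its type is on the 11.1.3 list (expected) with its handling if it is not (unexpected).

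| Event | 6.3.2 table: unexpected | 6.3.2 table: expected | Table after 11.1.3: unexpected | Table after 11.1.3: expected |
|---|---|---|---|---|
| Grade 2 | 10 calendar days | not required | 10 working days | not required |
| Grade 3, no hospitalization | 24 hours, then 5 calendar days | not required | 24-hour call, then 10 working days | not required |
| Grade 3, hospitalization | 24 hours, then 5 calendar days | 10 calendar days | 24-hour call, then 10 working days | not required |
| Grades 4 and 5 | 24 hours, then 5 calendar days | the same | 24 hours, then 5 calendar days | the same |

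In the first two rows both tables agree that the listed event needs no expedited report. An event directly attributed to 5-ALA is in this related group, so a DLT can fall in either row.

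**Hospitalized Grade 3.** Section 11.1.3 and the table after it say not required. The bullets in 6.3.1, 11.1.1 and 11.5 require a report whatever the expectedness and attribution, with Medwatch used within 24 hours. The 6.3.2 table, repeated in 11.5, gives 10 calendar days. The closing note of 6.3.2 and the timeline definitions in 11.5 then except protocol-specific exclusions from the hospitalization rule, without saying whether 11.1.3 is one. These places cannot all be followed.

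**Nausea and vomiting as the test case.** Section 11.1.2 caps expected nausea at Grade 2 and does not list vomiting. The balance-problems bullet in 11.1.3 adds both, as possible after surgery, with no cap. Section 11.5 points the other way: "Subjects will be assessed for any unexpected serious adverse events such as significant changes in vital signs, nausea, vomiting, rashes, skin eruptions". Section 12.1.1 singles out both for special attention. Section 2.1.4 cites a study in which 8% of patients vomited at 60 mg/kg and none at 30 mg/kg. So Grade 3 nausea, or Grade 2 or 3 vomiting, attributed to 5-ALA is outside the drug list but can enter the expected column through the surgical list.

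**The case against.** The strongest reply is that 11.1.3 describes risks of tumor removal, and most of its bullets name the procedure or the tumor as the cause. An event judged to be caused by 5-ALA is then arguably outside the list, and sections 11 and 11.5 reserve the phrase about 5-ALA-specific events for 11.1.2. This is a fair reading of intent. But 6.2 makes both lists expected without that condition, and the related row of the 6.3.2 table has an expected column. The text leaves the investigator to choose.

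A second reply is that other safeguards exist, and this stands. The DSMC meets after each cohort, discusses each adverse event and determines causality. Serious events and unanticipated problems go to it at once. Those tied to the protocol stop the study and go to the institutional review committee (SCRIHS) and the FDA. Section 11.6 requires FDA to be promptly informed of significant new drug risks. All events enter routine submissions, and the DLT rule does not depend on expectedness. None of these clearly sets a fixed expedited deadline for a non-serious Grade 2 or 3 event.

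A reader might infer that every Grade 2 or 3 listed event attributed to 5-ALA escapes expedited reporting. The documents do not support that. Grade 3 events that precipitate or prolong hospitalization are covered by 6.3.1, 11.1.1 and 11.5, and because treatment is inpatient (4.1), prolongation is a realistic route. The exemption sentence has no grade limit of its own, but both tables require expedited reports for expected Grades 4 and 5. Nor does a count of 17 surgical types against 3 drug effects measure risk: the 17 include recurrence and post-operative pain.

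The attribution scale in 6.2 and 11.5 refers to study treatment. Since 4.1 and 4.4 use treatment and therapy for 5-ALA dosing, the drug is probably meant. One clarifying phrase is enough.

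**Conclusion.** The point holds for listed events of Grade 2, and of Grade 3 without hospitalization or its prolongation, that are attributed to 5-ALA. The protocol as written asks for no expedited report, where the same event classed as unexpected would have a deadline. For hospitalized Grade 3 events the finding is a contradiction, not a clear exemption.

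The loss is speed of reporting. A reader might go further and conclude that DLTs would be missed or dose escalation misdirected. The documents do not support that, because these events still count under 4.2 and still reach the DSMC.

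A DLT without an expedited report is also not peculiar to 11.1.3: Grade 2 nausea attributed to 5-ALA is one under 11.1.2, apparently by design. The defect is that 11.1.3 extends this treatment to event types and grades that the protocol does not list as drug effects.

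The conclusion assumes that 6.2 is read literally. The documents give no rates for related events of these types and grades, so the number of reports affected cannot be estimated.

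**What to change.** 1. Amend 11.1.3 so that its exemption applies only to events attributed Unrelated or Unlikely to 5-ALA.
2. Amend 6.2 so that, for events Possibly, Probably or Definitely related to 5-ALA, only the 11.1.2 list with its grades counts as expected.
3. State in 6.2 and 11.5 that attribution means attribution to 5-ALA. A separate field for attribution to surgery is not needed.
4. Reconcile 6.3.1, 6.3.2, 11.1.1, 11.1.3, the table after 11.1.3 and 11.5 for Grade 3 events with hospitalization, and say whether 11.1.3 is a protocol-specific exclusion. Items 1 and 2 do not settle this for Unrelated or Unlikely events, where the three answers would remain.

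The cost is a wording amendment and a few more Medwatch reports. No dose, DLT definition or clinical procedure changes.
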